## Prevention of Respiratory Failure Addressing COVID-19 Epidemic (PREFACE Trial)

### *CHEAT SHEET*

#### Inclusion Criteria:

1. Males and Females 18 to 70 years of age
2. Lab confirmed COVID-19
3. Patients with progressive increase in supplemental oxygen requirements, developing acute hypoxic respiratory failure as defined by SaO2 < 93% on ≥6L supplemental oxygen.
4. Not on mechanical ventilation
5. D-Dimer > 1 µg/ml

#### Exclusion Criteria:

1. Active bleeding or high risk for bleeding (stroke within 14 days, gastrointestinal bleeding within 14 days, thrombocytopenia defined as platelet count <50 x10^3/µL, etc.)
2. Bleeding diathesis
3. Previously documented heparin induced thrombocytopenia
4. Patient on systemic anticoagulation for medical conditions which predate current admission: known prior VTE, atrial fibrillation, acute coronary syndrome.
5. If a patient is participating in any other clinical trial of an experimental treatment for COVID-19, the potential interaction of the trials will be reviewed by the study PIs for potential exclusion.
6. Pregnant females
7. Weight > 150 kg (rationale: enoxaparin dosing becomes less clear for patients greater than this weight)
8. Clinical contraindication as deemed by the attending physician

**Background:**

Coronavirus disease 2019 (COVID-19) is a novel respiratory viral infection, with the first cases appearing in Wuhan, China in December 2019. Patients can be asymptomatic, have mild symptoms, have more significant symptoms requiring supplemental oxygen or develop severe acute respiratory syndrome coronavirus 2 (SARS-CoV-2), leading to acute respiratory distress syndrome (ARDS). The growing public health concern is the number of patients that develop SARS-CoV-2, many of which develop ARDS requiring mechanical ventilator support and critical care management. As would be expected, this is the population with the highest mortality rate.

In addition to the progression of lung disease, SARS-CoV-2 patients develop a viremia with systemic manifestations. Incubation is reported to be 1-14 days. The lungs, gastrointestinal tract, and heart appear to be the most susceptible organ systems to increasing viral load. At approximately 7-14 days after onset of symptoms, there is a reported increase in tissue expression of ACE-2, the entry receptor for SARS-CoV-2. With the currently understood natural history of the disease, lung parenchymal changes progress with worsening of pulmonary symptoms, peripheral blood lymphocyte counts drop, and a significant increase in inflammatory factors can be found. (1-4)

It is at this second phase of disease progression that patients develop a hypercoagulable state, with D-dimer based coagulation factors appearing abnormal. During the development of dyspnea and progression of chest imaging the measurements of D-dimer increased from mild to significant. Additionally, prolongation of the prothrombin time (PT) and decrease of fibrinogen (FBG) and platelets is noted. Observations that some of the non-survivors had developed ischemic changes including ecchymosis of fingers and toes at the same time as the organ functions of the heart and kidneys deteriorated. This pattern is consistent with the hypercoagulable phase of DIC. (5) It has been suggested that COVID-19 can activate coagulation cascade through various mechanisms, leading to severe hypercoagulability, potentiating the development of systemic microthrombi, leading to the injury of major organ systems. (6,7)

In an epidemiologic study in China evaluating the Wuhan population, the investigators found that 17% of patients developed ARDS. (8) Another retrospective evaluation in Wuhan, China of 109 patients who died of complications of SARS-CoV-2 versus 116 patients who survived, reported that 89.9% of those who died had developed ARDS versus 7.6% in the group that survived. (9) In another study, it was identified that the median time from admission to ARDS was two days. (10) Historically in the United states the mortality rates of ARDS are 25% to 40%. (11) The initial reports strongly suggest that the development of ARDS as a result of SARS-CoV-2 may have a higher mortality rate than ARDS due to different etiologies.

There is very little information regarding the histopathological features in COVID-19 infections. In one study two patients who both underwent lung resection for adenocarcinoma were later found to be COVID-19 positive after the operation. (12) Review of the histopathology demonstrated non-specific edema, pneumocyte hyperplasia, focal inflammation, and multinucleated giant cells (no hyaline membranes). In another report of a patient who had died of COVID-19, histopathologic evaluation of the lung tissue demonstrated findings of diffuse alveolar damage with exudates, with predominately lymphocytic inflammation, multinucleated giant cells, and large atypical pneumocytes. (13)

ARDS is an acute diffuse, inflammatory lung injury, leading to increased pulmonary vascular permeability, increased lung weight, and loss of aerated lung tissue with hypoxemia and bilateral radiographic opacities associated with increased venous admixture, increased physiological dead space and decreased lung compliance. (14) The

definition includes an acute onset ( $\leq 1$  week), bilateral opacities consistent with pulmonary edema, a reduced  $\text{PaO}_2/\text{FiO}_2$  (P/F) ratio ( $<100$  severe, 100-200 moderate, 200-300 mild), not explained by fluid overload or congestive heart failure (CHF)

ARDS is the terminal path of various forms of lung injury. Pathologically this is observed as the development of alveolar injury due to diffuse alveolar damage. The cascade of events in the development and progression of ARDS causes the release of pro-inflammatory cytokines (tumor necrosis factor, interleukin (IL)-1, IL-6, IL-8). These events lead to recruitment of neutrophils to the lungs, which become activated with local release of toxic mediators (reactive oxygen species and proteases). This process causes damage of the capillary endothelium and alveolar epithelium leading to alveolar edema. (15) The progression of this process, leads to worsening impairment of gas exchange, decreased lung compliance, and increased pulmonary arterial pressure.

Lung compliance is the ability of the lung to stretch and expand. Pulmonary compliance ( $C_P$ ) is defined as the change in lung volume per unit change in pressure.

$$C_P = \Delta V / \Delta P$$

$\Delta V$  = Change in lung volume

$\Delta P$  = Change in lung pressure

Lung compliance can be measured as either static (volume changed divided by the plateau inspiratory pressure) or dynamic (volume change divided by peak inspiratory transthoracic pressure). In the intensive care unit, the static lung compliance is most commonly evaluated for patient evaluation and management. A standard compliance curve is graphed as volume to pressure. When the volume of the lungs is maximized (overdistended) the airway pressure is significantly increased as is expected. When the volume is low (at functional residual volume/atelectasis), airway pressure is reduced. Normal ventilation takes place through normal tidal breathing.

[figure not shown]

Figure from Respiratory physiology and Care, Wilson J, DiFiore JW. Pediatric Surgery (seventh Edition), 2012. Reproduced for research protocol without permission.

Diseased lungs, in which the compliance has dropped, leads to flattening of the compliance curve (overdistention) at much smaller volumes. Decreased lung compliance has strongly modified ventilation techniques, historically lung-protective strategies have developed for patients including moving to smaller and smaller tidal volumes with increased levels of positive end-expiratory pressure (PEEP).

In addition to traditional lung-protective strategies of ventilating with smaller lung volumes and higher PEEP pressure in ARDS, prone positioning of patients has been used successfully as a salvage therapy for refractory hypoxemia. Prone positioning was initially suggested to reduce atelectasis in the injured lungs, by reducing pleural pressure gradients and restoration of aeration to the recoverable dorsal lung segments. (16) There are multiple physiological processes, which occur in the lungs with prone positioning. In short, there is an improvement in ventilatory homogeneity through the lung in the prone position. Due to gravitational effects of pulmonary perfusion, improvement of the shunt fraction in patients prone increases by approximately 30%. (17,18,19) Prone positioning is recommended to be performed for 16 hours per day. When prone patients are returned to the supine position, the improvement in the PF ratio seen with prone positioning is reported to have prolonged benefit for at least four hours, with eventual return to the pre-prone condition. (20) There is anecdotal information in the literature and additionally through personal communications with treating physicians in Wuhan that there appears to be a significant benefit to oxygenation in patients with severe refractory hypoxemia using prone positioning.

### **Specific Aims:**

1. To identify an intervention that may contribute to fewer patients developing severe refractory hypoxemia.
  - a. Challenge: The current pandemic is causing a major stress to the medical establishment, leading to shortages of critical resources including but not limited to human, ventilators, hospital beds, and medications.
  - b. Approach: The protocol will use standard medications that are currently not part of the management strategies of patients with COVID-19 infections.
  - c. Impact: If the intervention provided at the suggested time works, fewer patients will develop severe refractory hypoxemia and respiratory failure potentially decreasing ventilator need, decreasing ICU bed utilization, and decreasing mortality.

### **Rationale for the Project:**

1. It has been noted both in the Chinese experience as well as by local physicians that patients with active COVID-19 infections tend to develop a hypercoagulable state, with frequent clotting of lines, dialysis catheters, and the development of signs of systemic thrombotic/microthrombotic activity, demonstrating findings similar to the reports by Taisheng Li, et al (5).
2. The patients who develop ARDS by P/F ratio criteria are demonstrating an atypical physiologic finding of relatively normal lung compliance with severe hypoxemia. Interestingly the only histopathologic studies available (13) gives descriptions of diffuse alveolar damage but does not describe intra-alveolar hyaline cast deposition with the other specifically identified changes, which could conceivably explain the finding of more compliant lungs identified clinically.
3. Prone positioning in ARDS is an accepted salvage therapy for severe hypoxemia. Typically, patients demonstrate improvement in oxygenation in the prone position, which should lead to protection of this effect for  $\geq 4$  hours in most patients. It has been observed that once supine again, there is near immediate deterioration to the same level of severe hypoxemia identified prior to prone positioning in COVID-19 patients.
4. When patients are admitted to the hospital to receive supplemental oxygen or require ventilation, they are all positioned in the supine position. This would alter the lung physiology, with the most dependent lung zones becoming dorsal rather than basal.
5. We therefore suggest that due to the hypercoagulable state found in patients with COVID-19 infections, severe hypoxemia develops due to the progression of pulmonary vascular thrombotic/microthrombotic disease in the dependent lung zones, which in the predominately supine position seen in patients in the hospital, would be the dorsal zone of the lung. As this process progresses it causes shunt physiology, identified with worsening hypoxia and low P/F ratios. Additionally, this proposed pathologic change would account for the non-ARDS lung compliance patterns noted in most patients. Lastly, this mechanism would additionally explain the rapid deterioration of oxygenation in patients when returned to supine after prone positioning.

### **Significance:**

Control / reversal of the suggested progressive thrombotic state found in patients with worsening hypoxia, respiratory failure, and ARDS, could lead to a disruption in the rapid clinical decline of patients with active COVID-19 infections interrupting the pathway of progressive hypoxic respiratory failure.

### **Subjects in the Project:**

#### Inclusion Criteria non vented:

1. Males and Females 18 to 70 years of age
2. Lab confirmed COVID-19
3. Patients with progressive increase in supplemental oxygen requirements, developing acute hypoxic respiratory failure as defined by SaO2 < 93% on ≥6L supplemental oxygen.
4. D-Dimer > 1 µg/ml

#### Exclusion Criteria:

1. Active bleeding or high risk for bleeding (stroke within 14 days, gastrointestinal bleeding within 14 days, thrombocytopenia defined as platelet count <50 x10^3/µL, etc.)
2. Bleeding diathesis
3. Previously documented heparin induced thrombocytopenia
4. Patient on systemic anticoagulation for medical conditions which predate current admission: known prior VTE, atrial fibrillation, acute coronary syndrome.
5. If a patient is participating in any other clinical trial of an experimental treatment for COVID-19, the potential interaction of the trials will be reviewed by the study PIs for potential exclusion.
6. Pregnant females
7. Weight > 150 kg (rationale: enoxaparin dosing becomes less clear for patients greater than this weight)
8. Clinical contraindication as deemed by the attending physician

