### **Project Design and Protocol:**

Open-label randomized controlled study with a 2:1 enrollment ratio of systemic anticoagulation using enoxaparin subcutaneous (or unfractionated heparin in those with a creatinine clearance (CrCl) <30 ml/m^2) in patients with COVID-19 and acute hypoxic respiratory failure.

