**Study Procedure:**

1. Patients admitted to HFH with suspected/identified COVID-19 infection will be reviewed daily
2. Those patients that fulfill the inclusion / exclusion criteria will be approached regarding participation in the study. If the patient is intubated, their designated representative will be approached regarding participation in the study.
3. If after answering all questions they agree to participate, an Informed Consent Form will be signed with a copy provided to the patient or their representative.
4. After enrollment, participants will be randomly assigned in a 2:1 ratio to the intervention or standard care control arm. Randomization will be stratified by stable/non-stable status and creatine clearance rate, using sequentially numbered, opaque, sealed envelope (SNOSE) technique for the allocation concealment.
5. Once enrolled, the primary patient history and laboratories will be reviewed, and data collected.
6. Orders for Enoxaparin or high intensity unfractionated heparin IV will be started within six hours of enrollment:
  - a. Options for stable patient (no procedures, hemodynamically stable):
    - i. CrCl  $\geq$  30 mL/min: Enoxaparin 1 mg/kg Q 12 hours
    - ii. CrCl of 15-29 mL/min: Enoxaparin 1 mg/kg Q 24 hours
    - iii. CrCl  $<$  15, rapidly fluctuating renal function, AKI/ESRD on IHD or CRRT: Heparin infusion at 12 units/kg/hr without initial bolus targeting aPTT 1.5-2.5 (55-75 seconds) normal range; dosing and monitoring per the HFH Low Intensity Heparin Protocol Guidelines. (21)
  - b. Options for unstable patient (anticipated procedures, hemodynamically unstable, severe critically illness):
    - i. Heparin infusion at 12 units/kg/hr without initial bolus targeting aPTT 1.5-2.5 (55-75 seconds) normal range
7. Duration of study anticoagulation:
  - a. No acute venous thromboembolism: anticoagulation throughout hospital stay and for six weeks post discharge.
  - b. New acute indication (DVT, PE, atrial fibrillation) for anticoagulation that develops during study treatment: 3 months; agent selection based on treatment team.
8. In the event of development of
  - a. Suspected or confirmed heparin induced thrombocytopenia without thrombosis (isolated HIT): (22-25)
    - i. Treat patient for 4 weeks with one of the following options given the clinical scenario:
      1. Options for stable patient (no procedures, hemodynamically stable):
        - a. CrCl  $\geq$  30 and weight  $>$  50 kg: Fondaparinux 2.5 mg SubQ Daily

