        - b. CrCl  $\geq$  30: Rivaroxaban 15 mg PO BID x 15 days, then 20 mg PO QD

- c. CrCl < 30: Apixaban 5 mg PO BID
  2. *Option for unstable patients (anticipated procedures, hemodynamically unstable, severe critically illness):*
    - a. Bivalirudin – goal PTT 1.5-2.5 times baseline PTT; dosing and monitoring per the HFHS HIT Guidelines. (Appendix A)
      - i. CrCl >60 mL/minute: 0.15 mg/kg/hr
      - ii. CrCl 30 to 60 mL/minute: 0.08 mg/kg/hr
      - iii. CrCl <30 mL/minute or dialysis: 0.05 mg/kg/hr
      - iv. CRRT: 0.07 mg/kg/hr
    - b. Suspected or confirmed heparin induced thrombocytopenia with thrombosis (HITT):
      - i. Treat patient for 3 months with one of the following options given the clinical scenario:
        1. *Stable patients (no procedures, hemodynamically stable):*
          - a. CrCl < 30: Apixaban 10 mg PO BID, then Apixaban 5 mg PO BID thereafter
          - b. CrCl ≥ 30: Fondaparinux
            - i. Weight < 50 kg: 5 mg SubQ Daily
            - ii. Weight 50-100 kg: 7.5 mg SubQ Daily
            - iii. Weight > 100 kg: 10 mg SubQ Daily
          - c. CrCl ≥ 30: Rivaroxaban 15 mg PO BID x 15 days, then 20 mg PO QD
        2. *Unstable patients (anticipated procedures, hemodynamically unstable, severe critically illness):*
          - a. Bivalirudin: goal PTT 1.5-2.5 times baseline PTT; dosing and monitoring per the HFHS HIT Guidelines
            - i. CrCl >60 mL/minute: 0.15 mg/kg/hr
            - ii. CrCl 30 to 60 mL/minute: 0.08 mg/kg/hr
            - iii. CrCl <30 mL/minute or dialysis: 0.05 mg/kg/hr
            - iv. CRRT: 0.07 mg/kg/hr
  9. The patients will be monitored after the initiation of therapy.
    - a. The first follow-up will be twelve hours after the start of anticoagulation.
    - b. Evaluation of clinical status will be completed twice daily to monitor progression of hypoxemia, respiratory failure, development of ARDS.
    - c. Daily laboratory testing including CBC with differential, electrolytes, PT, aPTT, INR, D-Dimer.
    - d. Ferritin, LDH, Triglycerides will be checked QOD as per Henry Ford Hospital COVID-19 Management guidelines.
  10. All patients who are in the control group will receive standard of care therapy inclusive of VTE prophylaxis and proning if part of routine care.

11. Post-discharge follow-up:
  - a. Patients will be maintained on anticoagulation upon discharge.
  - b. Patient contact 2 weeks post discharge
  - c. D-Dimer to be drawn at 4 weeks

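### Exclusion 4 stops at conditions that predate admission, so a patient already on treatment-dose anticoagulation for an indication found earlier in the same admission can be randomized, including to control

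*Protocol*

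**What the plan says.** Exclusion 4 appears in identical words in the Cheat Sheet and under Subjects in the Project: "Patient on systemic anticoagulation for medical conditions which predate current admission: known prior VTE, atrial fibrillation, acute coronary syndrome". The conditions after the colon illustrate the limit to conditions that predate admission; they do not extend it.

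Four other places in the protocol bear on the point:

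- **Exclusion 8** is a general clause: "Clinical contraindication as deemed by the attending physician".
- **Study Procedure, step 7b** sets the duration of anticoagulation for a "New acute indication (DVT, PE, atrial fibrillation) for anticoagulation that develops during study treatment".
- **Study Procedure, step 10** describes the comparator: "All patients who are in the control group will receive standard of care therapy inclusive of VTE prophylaxis". It says nothing about a control who is already on treatment-dose anticoagulation.
- **Project Design and Protocol** describes the trial as an "Open-label randomized controlled study with a 2:1 enrollment ratio of systemic anticoagulation using enoxaparin subcutaneous", with unfractionated heparin as the alternative in renal impairment.

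On timing, step 1 of the Study Procedure says: "Patients admitted to HFH with suspected/identified COVID-19 infection will be reviewed daily". Entry requires worsening hypoxia on supplemental oxygen and a D-dimer above 1 µg/ml, so randomization can come some time after admission. The Data Analysis section specifies intention to treat.

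**The concern.** The evident statistical purpose of an exclusion like this is to keep out patients who already receive the class of treatment under test. Tying it to when the condition arose, instead of to what the patient is receiving at randomization, leaves part of that purpose unmet.

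The case is foreseeable from the protocol itself. Its rationale is that these patients become hypercoagulable and form clots while in hospital, and step 7b names DVT, PE and atrial fibrillation as indications to expect. A patient diagnosed and anticoagulated early in the stay, who meets the oxygen and D-dimer criteria a day or two later, satisfies every inclusion criterion and no specific exclusion.

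What is at stake is the primary comparison of progression to mechanical ventilation. A control who continues treatment-dose anticoagulation is in substance treated like the intervention arm but counted as a control. This pulls the control rate toward the intervention rate and costs power.

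**Working it through.** **Step 1. Follow one patient through the rules.** Take a patient admitted without anticoagulation, diagnosed with a DVT on day 2, anticoagulated at treatment dose that day, and meeting the oxygen and D-dimer criteria on day 4.

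| Rule | Does it apply? |
|---|---|
| Inclusion criteria | Met |
| Exclusion 4 | No: the condition does not predate the admission |
| Exclusion 8 | Only if the attending physician judges there is a contraindication; the patient has an indication |
| Step 7b | No: the indication arose before study treatment began |

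The patient can be randomized to either arm.

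**Step 2. Reproduce the planned sample size.** Inputs from Justification for Number of Subjects or Data: control rate p1 = 0.25; relative reduction 30%, so p2 = 0.25 × 0.70 = 0.175; two-sided alpha 0.05; power 80%; arms of 687 and 344, that is k = 2. With the pooled-variance formula and no continuity correction:

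n(control) = [1.960 × √(p̄(1−p̄)(1+1/k)) + 0.8416 × √(p1(1−p1) + p2(1−p2)/k)]² / (p1−p2)²

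Here p̄ = (0.25 + 2 × 0.175)/3 = 0.20, so

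n(control) = [1.960 × √0.24 + 0.8416 × √0.25969]² / 0.075² = (0.9602 + 0.4289)² / 0.005625 ≈ 343.02.

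Rounding each arm up gives 344 controls and 687 in the intervention arm (2 × 343.02 = 686.04), a total of 1031. The plan's figure reproduces, and power at 344:687 is 80.1%.

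**Step 3. Dilute the control arm.** Let f be the share of controls already on treatment-dose anticoagulation at randomization. The documents give no value, so f is an assumption. Give these controls the intervention-arm rate and hold the intervention arm at 17.5%:

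p1(f) = (1−f) × 0.25 + f × 0.175 = 0.25 − 0.075f

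Apparent relative reduction = (p1(f) − 0.175)/p1(f)

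Power = Φ{[p1(f) − p2 − 1.960 × √(p̄(1−p̄)(1/344 + 1/687))] / √(p1(f)(1−p1(f))/344 + p2(1−p2)/687)}, with p̄ the average rate weighted by arm size.

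For f = 10%: p1(f) = 0.2425 and p̄ = (344 × 0.2425 + 687 × 0.175)/1031 = 0.1975. The numerator is 0.0675 − 0.0515 = 0.0160 and the denominator 0.0273. The ratio is 0.585 before rounding, and Φ(0.585) = 72.1%.

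| Assumed f | Controls affected (f × 344) | Control rate | Apparent relative reduction | Power |
|---|---|---|---|---|
| 0 | 0 | 25.0% | 30.0% | 80.1% |
| 2% | about 7 | 24.85% | 29.6% | 78.6% |
| 5% | about 17 | 24.6% | 28.9% | 76.3% |
| 10% | about 34 | 24.25% | 27.8% | 72.1% |

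**Step 4. Limits of the model.** It gives affected controls the average treated risk and adds no risk for the clot itself. It shows scale and does not forecast.

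**The case against.** The strongest objection concerns size. No share is given, and what the protocol does say suggests a small one. The Background cites a median of two days from admission to ARDS, so the window for a clot to be found and treated before randomization looks short. Specific Aims describes the study drugs as not at that time part of COVID-19 management, so routine treatment-dose use before entry is not described. At 2% of controls the loss is 1.5 percentage points of power. This stands: the size is unknown and may be minor. A reader might carry the same formula to 20% of controls, where power is 63%, but nothing in the documents supports so large a share.

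The second objection is that exclusion 8 lets the attending physician keep such patients out. It may do so in some cases. It is discretionary, though, and it speaks of contraindication. It does not close the gap, and it could be applied unevenly.

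Three stronger readings are tempting, and the documents do not support them.

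- **That controls would be held to prophylaxis despite a diagnosed clot.** Step 10 says standard care includes prophylaxis; it does not cap care there. Nothing tells staff to stop or withhold treatment, and the trial is open-label.
- **That a clot known at entry would be counted under the secondary VTE endpoint.** The protocol directs no such count, and the counting window is commonly left to the statistical analysis plan, which is not shown.
- **That every patient with an indication should be excluded.** Exclusion 4 requires the patient to be on anticoagulation. Extending it to untreated indications would remove patients whom the current wording admits, which goes beyond this gap.

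**Conclusion.** The point holds as a gap in the eligibility wording. Exclusion 4 ends at admission and step 7b begins with study treatment, so anticoagulation started between the two is governed by neither. The affected patients can be randomized, and those allocated to control weaken the primary contrast under intention to treat.

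That conclusion follows from the text and needs no assumption about frequency. The loss of power does: 1.5, 3.8 or 8.0 percentage points if 2%, 5% or 10% of controls are affected, carry the intervention-arm rate and stay on treatment-dose anticoagulation. The planned sample size itself is correct for its stated inputs. Eligibility is set in the protocol, so this is a stated rule drawn too narrowly and not a detail deferred to the analysis plan. It is worth correcting because the correction is cheap, even if the number of patients proves small.

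**What to change.** In both exclusion lists, make criterion 4 turn on status at randomization: exclude any patient then receiving treatment-dose systemic anticoagulation, whether the condition predates the admission or arose during it. Saying treatment-dose keeps patients on routine VTE prophylaxis eligible, as they must be, since prophylaxis is part of the control arm.

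Reconcile the new wording with step 7b so that no interval is left between the two rules. Step 6 allows up to six hours from enrollment to the start of study anticoagulation, so the point at which 7b takes over should be stated.

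The cost is one sentence in two places, a check of step 7b, and the loss of a small number of otherwise eligible patients who would give little or no contrast as controls. The sample size calculation needs no change. How such patients are treated is left to the investigators.
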